## Appendix I

Example of printout provided to participants to remind them of their maximum and target heart rate as well as their weekly exercise goals. The example is for an 80 yearold participant.

**Maximum heartrate: 140 beats/minute**

**Target heartrate: moderate = 70 to 98 beats/min**  
**vigorous = 98 to 119 beats/min**

Weekly goal: 150 minutes of moderate exercise  
or  
75 minutes of vigorous exercise

### **Overexerting Yourself**

Beware of pushing yourself too hard too soon or too often. If you are short of breath, are in pain or cannot work out as long as you'd planned, your exercise intensity may be too high for your fitness level. Build intensity gradually.

## Appendix II

Rating of Perceived Exertion (RPE) scale. This will be attached to the top visible surface of the bike display.

Rating	Description
0	Nothing At All
0.5	Very, Very Light
1	Very Light
2	Fairly Light
3	Moderate
4	Somewhat Hard
5	Hard
6	
7	Very Hard
8	
9	
10	Very, Very Hard (Maximal)

## Appendix III

**Exercise Log**

Start Date: \_\_\_\_\_

Week: \_\_\_ 1 \_\_\_\_\_

	Sunday	Monday	Tuesday	Wednesday	Thursday	Friday	Saturday
Did you bike today							
Minutes of cycling							
Estimated Average Speed							
RPE during activity							
RPE 5 minutes after							
Highest Heartrate							
Did you have any discomfort during the session?							

Did you do any additional physical activity this week?

Do you have any concerns about this weeks cycling sessions?

Did you fall this week? If yes, please describe the falls.

# 1. Summary

The benefits of exercise for individuals with Parkinson disease (PD) have been well documented; however, individuals with PD living in rural and underserved urban settings are largely unable or unwilling to participate in group exercise programs due in large part to their distance from such programs and financial considerations. Additionally, community based programs which provide social support and engagement have been shown to benefit elderly individuals as well as individuals with pathology, but are equally unattainable to this group. Taking the exercise to these individual via telemedicine or tele-exercise may be an ideal means of delivering this type of intervention.

The long-term goal of this project is to improve outcomes for underserved populations of individuals with Parkinson disease (PD) by providing access to in-home physical activity via a telehealth approach. Approximately one million Americans currently live with a diagnosis of PD and it has been estimated that delaying the progression by 20% would result in a \$75,891 savings per individual based on reduced health care costs, income maintenance, increased duration of life and improved quality of life. However, individuals with PD of lower socioeconomic status, people of color and rural dwelling seniors have been critically underserved by clinical and academic programming resulting in poorer health outcomes.

These two studies will examine: 1) the Reach, Effectiveness, Implementation and Maintenance and 2) the optimal delivery method for an in-home exercise intervention program for individuals with PD living in underserved communities. We will deliver a managed and meaningful exercise intervention that not only addresses the benefits of physical activity for individuals with PD, but also offers a social connection to research staff outside of the participant's typical caregiver(s).

## Study 1

Examine the reach, effectiveness and maintenance of an in-home, partnered cycling program for underserved individuals with PD.

## Study 2

Examine the effects of social engagement during in-home exercise on a small sample of individuals with Parkinson Disease (PD). This pilot investigation will directly measure the effect of social support and engagement for rural dwelling individuals with PD.

### 3. Participants Safety

#### 3.1 Potential Risks and Benefits for Participants

##### Potential Risks:

Physical: Common physical risks include muscle soreness, fatigue and shortness of breath. Less common physical risks include falls, heat intolerance, and skin irritation from the activity monitor. Rare but possible risks include cardio-vascular related events (sudden cardiac arrest, myocardial infarction, and stroke).

Psychosocial: Potential psychosocial risks include loss of confidentiality, frustration, embarrassment, depression or identification of suicidal thoughts.

##### Potential Benefits:

We do not yet know the full extent to which exercise may benefit individuals with Parkinson disease. Recent evidence suggests that exercise is beneficial to some individuals with PD in some cases. Some of the possible benefits may include improvements in physical function, quality of life, number of falls, balance, psychological factors including depression and non-motor features of PD.

#### 3.2 Adverse Event (AE) Definition

Adverse event (AE) means any untoward or unfavorable medical occurrence in a human subject or others that happens during or after participation in a research study.

An abnormal heartrate, perceived exertion rating, fall or other data point will not be assessed as an AE unless that value leads to therapeutic intervention, emergency medical service or is considered by the investigator to be a clinically significant change from baseline. These AEs will be entered into the study database.

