A tablet will be installed and mounted to the recumbent bike. A remote connection will be made to an individual at the UW to test the Skype connection and show the participant how to use the technology. This testing will lessen the likelihood of study dropout due to frustration with the technology component. An additional failsafe has been built into the computer system which allows us to remotely control the software and assist the participant if necessary. For privacy, we will not be able to access the machine without the participant clicking the allow button on the screen.

The selected recumbent bike has been chosen based on a number of factors which make it safe, user friendly and allow for the tracking of the desired speed and duration data. The bike weighs over 100 pounds and has a wide footprint to prevent tipping as well as a low ground clearance step through to allow individuals with PD to get on and off the bike without falling. The saddle is a wide padded seat with a fully supportive backrest to promote comfort but also maximize rider safety. Pulse sensors are located on the display mount

[figure not shown]

Figure 1. Movement of participants through the study.

and seat handles and pulse readings are incorporated into the software which allows for real-time tracking of the speed and resistance settings of the cycle. Additionally, this bike comes with a large digital display and preprogrammed cycling sessions that will allow a programmed and progressive exercise plan to be implemented after the 6-month group cycling program ends.

Scheduled training sessions will occur in the individual's home with digital display connecting the individual with PD to a member of the research team. Training sessions will occur three times per week for 6 months. Each training session will consist of up to 30 minutes of cycling at a target speed with a 2-minute warm-up session, and a 2-minute cool down at the end of the session. Actual intervention times will be based on the individual's endurance level and will increase over the sessions. The initial target speed will be at 110% of the average pace established by the individuals during the first testing session (10% above the self-selected velocity). Target velocities for future training sessions will be based upon the average of the previous week's training sessions. It will be the job of the research assistant to help the individual attain and maintain their target velocity during testing.

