For both studies, we will employ a  $2 \times 2$  repeated measures ANOVA with time and intervention as the factors, to determine the outcomes of the cycling intervention effectiveness aims. Additionally, we will use a time (posttest to 3-month follow-up) by group to examine the effectiveness of the health coach maintenance model. Variables of interest include: total number of completed sessions and session duration; PASS scores, walking velocity, stride length, base of support; gait variables (velocity, stride length, base of support and % of time in double support) and MiniBESTest scores as well as number of falls; and mean daily step count.

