#### 3.5.2 Relationship to Study Intervention

For all collected AEs, the PI will determine the AE's causality based on temporal relationship and her judgment. The degree of certainty about causality will be graded using the categories below.

- **Definitely Related** – Clearly related to the study procedures and other possible contributing factors can be ruled out.
- **Probably Related** – Likely related to the study procedures and the influence of other factors is unlikely.
- **Possibly Related** – Possibly related to the study procedures and there are other factors that could be equally likely.
- **Unlikely to be related** – Doubtfully related to the study procedures and there is another likely cause.
- **Unrelated** – Clearly not related to the study procedures and/or evidence exists that the event is definitely related to another cause.

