#### 3.5.3 Expectedness to Study Intervention

The Principal Investigator (PI) will be responsible for determining whether an AE is expected or unexpected.

For studies not evaluating an investigational drug or device, an AE will be considered unexpected if the nature, severity, or frequency of the event is not consistent with the risk information previously described in the protocol, the IRB application, or the informed consent document.

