### 3.6 Collection and Reporting of AEs, SAEs & UPs

Study participants will be instructed to contact the PI if any serious or unexpected adverse event occurs. Reported AE's will be recorded in detail in an AE case report form.

Adverse events that occur or are discussed during monitored sessions will be recorded by the study team and the PI will be notified as soon as possible. Events occurring outside of the monitored sessions or by individuals assigned to the solo cycling group will be identified by weekly calls with the participants and review of the exercise logs every four weeks. Any adverse events will be discussed at weekly research team meetings and will be reviewed to determine whether a change in protocol is necessary.

AE/SAEs that meet the definition of an unanticipated problem will be reported to the IRB within 14 business days. Events that are immediately life threatening, severely debilitating to other current subjects or resulted in a death will be reported to the IRB Chair or IRB Director via telephone or email within 24 hours (1 business day) of site awareness.

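### The AE definition leaves minor falls on the study bike outside AE grading and weekly AE review by default, although falls are a named risk of the exercise

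*Combined protocol and SAP*

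**What the plan says.** Section 3.2 of the Data and Safety Monitoring Plan opens with a broad definition of an adverse event and then narrows it: "An abnormal heartrate, perceived exertion rating, fall or other data point will not be assessed as an AE". Three exceptions follow: the finding leads to treatment, it brings in emergency services, or it is "considered by the investigator to be a clinically significant change from baseline". The rule is the same wherever the fall happens.

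The same plan lists falls among the physical risks in section 3.1: "Less common physical risks include falls, heat intolerance, and skin irritation from the activity monitor". The protocol body repeats this in its section on minimising risk during exercise. The Study 1 Intervention section gives the bike's low step-through as a safety feature, chosen "to allow individuals with PD to get on and off the bike without falling"; the Study 2 Intervention section says the same.

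Grading and review are written for adverse events. Section 3.5.1 grades the severity of AEs. Section 3.5.2 on relatedness begins "For all collected AEs, the PI will determine". Under section 3.5.3 "an AE will be considered unexpected if the nature, severity, or frequency of the event is not consistent with the risk information". Section 3.6 takes AEs to the weekly team meeting, where they "will be reviewed to determine whether a change in protocol is necessary".

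In Power and Statistical Analysis, falls appear as one count in the list of variables: "MiniBESTest scores as well as number of falls; and mean daily step count".

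**The concern.** A fall from the bike, or while getting on or off it, is the most direct evidence on whether the step-through design works as a safeguard. If the person gets up unhurt and needs no treatment, the rule treats that fall like a stumble in the garden, and by default neither is an AE. For daily-life falls in a fall-prone population that is sensible, because it avoids a flood of uninformative AE forms. For falls on study equipment the case is weaker, since relatedness is exactly the question one would want answered.

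Two things are at stake. During the study, a run of minor bike falls need not enter the review in which protocol changes are considered, unless someone chooses to escalate it. Afterwards, a pilot meant to inform a larger trial would have no planned summary of how often the bike was involved in a fall.

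This matters most for rides that nobody watches: Study 2 solo sessions, most Study 1 maintenance rides (coach contact is 15 minutes every other week, for half the participants), and the optional extra rides offered to participants in both studies.

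**Working it through.** No arithmetic applies. The point turns on the path a fall takes through the documents. The case to trace is a fall while mounting, riding or dismounting the study bike that is untreated, not attended by emergency services and not judged clinically significant.

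1. **Captured?** Yes. Study 1 has weekly falls contacts throughout, including the control and maintenance periods. Study 2 has a weekly falls assessment, by telephone for the solo group. The Appendix III log asks for a description of any fall, next to daily cycling entries. The fall-history questionnaire, which covers mechanisms, is repeated at posttest.
2. **Seen by the PI?** Probably, if the participant writes it down. Section 6.1 has the PI review the logs every four weeks for adverse events.
3. **Assessed as an AE?** Not by default (section 3.2).
4. **Graded for severity?** Not routinely; section 3.5.1 covers AEs.
5. **Graded for relatedness?** Not routinely; section 3.5.2 covers collected AEs.
6. **Tested for expectedness, including frequency?** Not routinely; section 3.5.3 covers AEs.
7. **Taken to the weekly AE discussion?** Not routinely; section 3.6 covers AEs.
8. **Counted in the analysis?** Yes, within the number of falls, pooled with all other falls. No split by setting is mentioned.

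Now vary the case. If the participant falls in a monitored session and hits the head, cannot get up or cannot move limbs, the emergency protocol requires a 911 call, so the emergency-service exception applies. If the fall is treated, the first exception applies. If it causes an untreated injury, the opening definition in section 3.2 could make that injury an AE, but the text does not say so. What remains is mainly the minor, untreated fall.

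The third exception does not reliably close the gap. It is discretionary, and a test of change from baseline suits a heart rate better than a single fall.

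**The case against.** The strongest reply is that several safeguards already surround these falls, so the gap is only one of labelling. The PI carries weekly responsibility for safety (section 6) and reviews logs that ask about falls, discomfort and concerns with the week's cycling. In monitored sessions, significant discomfort or a worrying comment ends the session, and follow-up calls are provided for. The unanticipated-problem definition (section 3.4) and the study stopping rules (section 5.2) are not confined to AEs. A cluster of bike falls could therefore reach the person who holds the discretion in section 3.2.

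Most of this stands, and it rules out a stronger reading. A reader might infer that bike falls go unrecorded or unseen, or that a cluster would certainly be missed. The documents do not support that. What they leave out is a routine step. The log review looks for adverse events, and section 3.2 says a minor fall is not one by default. The unanticipated-problem route needs the event to be unexpected; since falls are a described risk, that would usually rest on severity or frequency, and no stated step counts falls on the bike.

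Two further objections are fair. The analysis section describes no AE table for any kind of event, so the lack of a bike-fall table is general silence and does not single out falls. And the weekly falls questionnaire is not reproduced; it may already record circumstances. Even so, nothing requires that information to be graded or reported.

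**Conclusion.** The point holds in a limited form. By default, section 3.2 keeps minor falls on the study bike out of AE assessment, and with that out of routine grading and the weekly AE review, although falls are a named risk of the exercise. It is an optional improvement to a stated safety rule.

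Its size cannot be given as a number. The documents supply no expected frequency of bike falls and propose no rate of falls per ride, so any percentage would describe something the plan does not estimate. Nothing is irretrievably lost, because the captured descriptions would allow later coding.

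A reader might also infer that the falls outcome is compromised. It is not: total falls by arm is a valid outcome whether or not individual falls are also AEs.

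The conclusion assumes that section 3.2's general wording covers falls on the bike, which it does not mention but does not exempt, and that no rule in the material not shown requires these falls to be assessed.

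**What to change.** Amend section 3.2 so that any fall while mounting, riding or dismounting the study bike is assessed as an AE, treated or not, and state that any injurious fall is an AE wherever it happens. Keep minor daily-life falls excluded. In Power and Statistical Analysis, leave total falls as the randomised outcome.

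Add a short descriptive report of ride-related falls: the number of falls, the number of riders affected and a brief narrative of each, coded from the weekly falls contacts and the logs. Do not compute a rate per ride. If the weekly questionnaire does not already record circumstances, one tick-box would do (getting on, riding, getting off, not on the bike).

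The cost is some wording, the coding of descriptions already requested and a few more AE forms, with no new visits or staff. There is one statistical drawback to state openly. In Study 1's first six months only the cycling arm has the bike, so bike-fall AEs can arise in that arm alone. Detection also differs: falls are seen live in some sessions and self-reported in others, notably between the social and solo groups of Study 2. These events should therefore be listed separately and not compared between arms.

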#### 3.3 Serious Adverse Event (SAE) Definition

An adverse event is considered "serious" if, in the view of either the investigator or sponsor, meets any of the following criteria:

- Result in death
- Are life-threatening
  - (Refers to an AE in which the participant was at risk of death at the time of the event. It does not refer to an event, which hypothetically, might have caused death if it were more severe.)
- Requires an inpatient hospitalization or prolongation of an existing hospitalization
- Result in persistent or significant disability or incapacity.
  - (Disability is defined as a substantial disruption of a person's ability to conduct normal life functions.)
- Result in a congenital anomaly/birth defect.
- Constitute, based upon appropriate medical judgment, an event that may jeopardize the participant's health and may require medical or surgical intervention to prevent one of the other outcomes listed above.

#### 3.4 Unanticipated Problem (UP) Definition

The Office for Human Research Protections (OHRP) considers unanticipated problems involving risks to participants or others to include, in general, any incident, experience, or outcome that meets all of the following criteria:

- The incidence, experience, or outcome is unexpected given the research procedures described in protocol-related documents (e.g., the study protocol, the consent documents) and the characteristics of the subject population being studied. An event may be considered unexpected if it exceeds the nature, severity, or frequency described in the study-related documents.
- The incidence, experience, or outcome is related or probably related to participation in the research study. Probably related means the incidence, experience, or outcome is more likely than not to be caused by the research study procedures.
- The occurrence of the incidence, experience, or outcome suggests that the research places participants or others at a greater risk of harm (physical, psychological, economic, or social) than was previously known or recognized.

### 3.5 Classification of an Adverse Event

#### 3.5.1 Severity of Event

All AEs will be assessed by the PI using the Common Terminology Criteria for Adverse Events (CTCAE) Version 5., each event is searchable using the Safety Profiler website (<https://safetyprofiler-ctep.nci.nih.gov/CTC/CTC.aspx>). For AEs not included in the protocol defined grading system, the following guidelines will be used to describe severity.

- **Mild** – Events require minimal or no treatment and do not interfere with the participant's daily activities.
- **Moderate** – Events result in a low level of inconvenience or concern with the therapeutic measures. Moderate events may cause some interference with functioning.
- **Severe** – Events interrupt a participant's usual daily activity and may require systemic drug therapy or other treatment. Severe events are usually potentially life-threatening or incapacitating.
- **Life Threatening** – Places the patient or subject at immediate risk of death. It does not include an adverse event that, had it occurred in a more severe form, might have caused death.
- **Death**

#### 3.5.2 Relationship to Study Intervention

For all collected AEs, the PI will determine the AE's causality based on temporal relationship and her judgment. The degree of certainty about causality will be graded using the categories below.

- **Definitely Related** – Clearly related to the study procedures and other possible contributing factors can be ruled out.
- **Probably Related** – Likely related to the study procedures and the influence of other factors is unlikely.
- **Possibly Related** – Possibly related to the study procedures and there are other factors that could be equally likely.
- **Unlikely to be related** – Doubtfully related to the study procedures and there is another likely cause.
- **Unrelated** – Clearly not related to the study procedures and/or evidence exists that the event is definitely related to another cause.

#### 3.5.3 Expectedness to Study Intervention

The Principal Investigator (PI) will be responsible for determining whether an AE is expected or unexpected.

For studies not evaluating an investigational drug or device, an AE will be considered unexpected if the nature, severity, or frequency of the event is not consistent with the risk information previously described in the protocol, the IRB application, or the informed consent document.

